- [name], FCPS trainee (Obstetrics & Gynaecology), King Edward Medical University /Lady Willingdon Hospital, Lahore, Pakistan
- [name], Director of Medical Education, Institute of Public Health Pakistan

Settings: Lady Willingdon Hospital Lahore, Pakistan

Address: [name]

[contact]

Affiliated University: King Edward Medical University, Lahore, Pakistan (KEMU)

Hospital type: Government Teaching Hospital

Background

The urinary bladder injury is a rare but important complication of caesarean section (C-section). The decreasing trend of vaginal birth after C-section has led to an increased number of women with multiple C-sections.¹ After caesarean delivery, adhesions may develop between bladder and uterus (46% - 65% after primary C-section) which cause difficulty in identification and dissection of the bladder flap during the next operative delivery.^{2,3} The rate of bladder injury increases with the increasing number of C-sections being 0.13% for the first C-section, 0.09% for the second, 0.28% for the third, 1.17% for the fourth, 1.94% for the fifth, and 4.49% for the sixth caesarean delivery.⁴ The incidence of bladder perforation has been reported to be three times higher in women with the previous C-section compared to the women with first C-section (0.81% vs. 0.27%).⁵ Most bladder injuries occurred secondary to the extensive adhesive disease at the time of opening the peritoneal cavity and during the creation of the bladder flap.⁵ Bladder injury has been reported to occur with an overall incidence of 0.46% in a local Pakistani study, 0.44% in Saudi Arabia, 0.67% in Mumbai and 0.08 to 0.94% in international studies in C-section cases.⁶⁻¹¹

Tulandi and co-workers have proposed a scoring system of adhesions between bladder and uterus.¹²

Adhesions of previous C-section Between uterus and bladder	Consistency of the adhesions	<3 cm	3–6 cm	>6 cm
		Filmy	1	2
Dense	4	8	16	

Tulandi, T. & Lyell, D.J. *Gynecol Surg* (2013) 10: 25. <https://doi.org/10.1007/s10397-012-0765>

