Based on previous statistics of the target population (women with adhesions) in our hospital, about 400 subjects are expected to present during the study period. With this population, the sample size is calculated to be 107 for each group at 95% confidence level and 80% power, allowing a 10% drop out rate (Raosoft, Inc 2004; online sample size calculator for proportions). Therefore, a total of two hundred and fourteen patients fulfilling the eligibility criteria will be included in the study.

Subjects

The subjects of the study will be selected in two steps. In the first step, the women who will meet the preoperative study criteria and give the preoperative informed consent will be invited to participate in the study. In the second step, during C-section, the volunteers who will fulfil the inclusion criteria of adhesions will be enrolled in the study.

Preoperative study criteria

Inclusion criteria:

- Healthy pregnant women of any age
- Two or more previous C-sections
- Gestational age between 38-40 weeks (confirmed by dating scan)
- Provide written informed consent to participate in the study

Exclusion criteria:

- Patients with medical disorders
- Placenta previa on Ultrasonography

- Women experiencing micturition problems (dysuria, frequency, urgency, urinary retention, incontinence) before the study.
- Women who refuse to participate in the study.

The perioperative criteria of the study are

- Dense pelvic adhesions of Tulandi score 4 and above,
- adhesions covering the bladder and lower segment of the uterus so that empty bladder will not be identified among the adhesions.
- The lower segment cannot be approached without adhesiolysis.
- Adhesions will be encountered either at entry into the peritoneal cavity or before the creation of the bladder flap.
- The women with bladder injury prior to enrolment will be excluded from the study.

Recruitment procedure and consent for the study

The recruitment of subjects will be carried out over a period of 21 months (one year and nine months).

Subjects of the study will be selected in two steps.

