The second step of recruitment: The subjects of the study will be selected during c-section by purposive sampling and only those subjects who will fulfil perioperative criteria of the study will be selected. The primary surgeons of the C-section will be 2nd and 3rd-year residents of Lady Willingdon Hospital. If dense adhesions will be encountered during opening the peritoneal cavity or before the separation of bladder flap, the primary surgeons will hold the operation and call the principal surgeon (Assistant [name] and Gynaecology) to carry out adhesiolysis and complete the operation. The Principal surgeon will examine the adhesions and enrol the subjects in the study and perform randomization according to the random number envelop if perioperative criteria for adhesions will be fulfilled. (See [Entry Form](#))

The same Principal surgeon will recruit subjects after carrying out grading of adhesions, perform adhesiolysis and complete the operation with primary surgeons to avoid bias.(See [Fig 1](#))

Randomisation procedure

The Principal surgeon will randomize the calculated sample size into cysto-inflation and control groups by parallel assignment. They will write the random numbers (downloaded from the internet) on closed envelopes with the assigned groups inside. The closed envelopes will be serially placed with the smallest number uppermost, in random number file. The file will be kept in the safe custody of theatre in-charge nurse before starting recruitment for the study. If the women will fulfil the eligibility criteria, the Principal surgeon will recruit her in the study. The theatre in charge nurse will take out uppermost envelope from the subject's file. She will be open the envelope and disclose the group to the principal surgeon. Then, she will close the envelope again and place it below all the envelopes. The theatre staff nurse will also provide the setup for cysto-inflation. At the end of the operation, she will get the Entry Form signed by the Principal surgeon and hand it over to the study team. The study team medical officers in the theatre will enter the random number of each subject on her documents including Hospital Admission File, Consent Form, Trial Entry Form and Outcome Form.

Blinding

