there while the surgeon holding the tubing will inflate the balloon of the urinary catheter with 10cc distilled water. The theatre attendants will then correct the position of the patient again to straight leg position. The urinary catheter will be kept elevated as long as the patient will be draped with sterilized sheets for operation by the other surgeon. Then, the catheter end near the urinary port will be fixed to the patient sheet in front of the thigh to carry out cystinflation conveniently and attached to the urine bag for drainage.

Adhesiolysis

If adhesions will be encountered during opening the peritoneal cavity or before the separation of bladder flap, the primary surgeons will hold the operation and call the principal surgeon to carry out adhesiolysis and complete the operation. The Principal surgeon will grade the adhesions according to Tulandi's classification and if the woman will fulfil perioperative criteria for adhesions, the Principal surgeon will enrol her in the study as subject and perform randomization into cystoinflation and control groups according to her random number envelope. Adhesiolysis will be performed with the inflated bladder in cystoinflation group, and with the empty bladder in the control group.

Cystoinflation group: The adhesiolysis in cystoinflation group will be performed by bladder retro-fill. Cystoinflation (bladder retrofill) will require normal saline drip and a 60cc bladder wash syringe and an artery clip. In cystoinflation group, the bladder will be retro-filled with 300cc saline by the assigned house officer under strict aseptic measures at the rate of 60cc in one minute. Meanwhile, the principal surgeon will identify the margins of the bladder among adhesions. The catheter will be clamped with an artery clip after filling the bladder with 5 fillings of the syringe. The surgeon will stretch the adhesions by upward traction on the surface of the uterus with a sponge and counter-traction on adhesion with elices forceps or sponge and perform adhesiolysis by sharp dissection with a fine dissecting scissor. The adhesiolysis will be performed until the bladder surface can easily be pushed down. Thereafter, the house officer will attach the urine drainage port of the catheter with the tubing of the urine bag and remove the artery clip to empty the bladder. The surgeon will then push the bladder downward with Doyen's retractor to improve visualization in the surgical field and complete the C-section.

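### The exclusion for bladder injury before enrolment is tied to when the injury happened, not when it was recognised, so nothing stops its use after allocation, where it would mainly remove cystoinflation cases

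*Combined protocol and SAP*

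**What the plan says.** - **Subjects, perioperative criteria.** The last item reads "The women with bladder injury prior to enrolment will be excluded from the study". The same list requires "adhesions covering the bladder and lower segment of the uterus so that empty bladder will not be identified among the adhesions".
- **Background.** "Most bladder injuries occurred secondary to the extensive adhesive disease at the time of opening the peritoneal cavity"; the sentence goes on to name creation of the bladder flap as the other time. No split between the two is given.
- **Recruitment procedure, second step.** Second- and third-year residents open the abdomen. On meeting dense adhesions, "the primary surgeons will hold the operation and call the principal surgeon", who grades the adhesions and enrols.
- **Randomisation procedure.** If the woman is eligible she is recruited and the theatre nurse takes the top envelope: "She will be open the envelope and disclose the group to the principal surgeon". The nurse obtains the principal surgeon's signature on the Entry Form at the end of the operation. That form has an Eligible field but none for bladder status before allocation.
- **Adhesiolysis, Cystoinflation group.** "In cystoinflation group, the bladder will be retro-filled with 300cc saline by the assigned house officer", while the surgeon looks for the bladder margins and before dissection starts.
- **Control group.** The catheter drains freely throughout. A dye test is done in either group, but only on suspicion of injury.
- **Outcome.** Bladder injury rate is the percentage of subjects injured in each group, found by direct observation during surgery.
- **Statistical analysis.** The one rule on who is analysed concerns women who do not return for follow-up. There is no intention-to-treat statement.
- **Project summary.** The technique counts as effective if its injury proportion is below half that of control.

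**The concern.** An injury made by the residents on entry precedes enrolment. Because eligibility describes a bladder that cannot be picked out, and no bladder check before the envelope is described, such an injury can be unseen when the woman is enrolled.

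The arms then differ in how it comes to light. With cystoinflation, a leak during filling appears before any adhesiolysis, so it can be dated to before enrolment and literally meets the exclusion. In control, the same injury would usually surface during or after adhesiolysis, when it can no longer be dated and counts as an outcome.

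If the exclusion were applied at that stage, women would leave the analysis because they had the primary outcome event, and mostly from one arm. That lowers the cystoinflation rate even when the technique does nothing. Missed detection is a different problem: here an injury that was found would be dropped from the count.

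**Working it through.** The plan has no figure of its own on this point. The check first asks what the text allows, then how much it could matter.

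**1. What the text allows**

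| Step | Before the envelope | After the envelope |
|---|---|---|
| Eligibility | Assessed by the principal surgeon | Entry Form signed at end of operation |
| Bladder visibility | "so that empty bladder will not be identified among the adhesions" | Filled in one arm, empty in the other |
| Knowledge of arm | None | Principal surgeon knows |
| Rule for an injury judged to predate enrolment | Exclude | None stated |

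The bottom right cell is the gap: no sentence says whether such a woman is kept or removed.

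**2. Inputs**

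- From the documents: 107 per arm; success if the cystoinflation proportion is below 0.5 of control; highest cited injury rate 4.49% (sixth caesarean, Background).
- Assumed: *u*, the proportion of women with an unseen entry injury; *a*, the risk of adhesiolysis injury in the rest. Both are equal in the two arms, so there is no true effect.
- Also assumed unless stated otherwise: every unseen entry injury is shown by filling and removed from the cystoinflation arm, and every one is found and counted in control.

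**3. Expected ratio under one-sided removal**

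Control risk = *u* + *a*(1 − *u*). Cystoinflation risk among the women kept = *a*. Apparent risk ratio = *a* / [*u* + *a*(1 − *u*)].

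- *a* = 4%, *u* = 0.5%: 0.04 / (0.005 + 0.0398) = 0.89; about 107 × 0.005 = 0.5 women removed.
- *a* = 4%, *u* = 3%: 0.04 / (0.03 + 0.0388) = 0.58; about 107 × 0.03 = 3.2 women removed.

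The true ratio is 1.00 in both.

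**4. Chance of meeting the 50% rule with no true effect** (simulation, 400,000 trials per row, 107 per arm)

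| *a* | *u* | All injuries counted | Entry injuries removed from cystoinflation |
|---|---|---|---|
| 4% | 0.2% | 14% | 16% |
| 4% | 0.5% | 13% | 18% |
| 4% | 1% | 12% | 22% |
| 4% | 3% | 8% | 39% |
| 4% | 5% | 6% | 57% |
| 10% | 3% | 3% | 13% |

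**5. Relaxing the assumptions** at *a* = 4%, *u* = 3%. The 39% falls to 19% if only half of the entry injuries are removed from the cystoinflation arm, and to 26% if all are removed there but only half surface in control.

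**6. Cross-check by exact binomial enumeration**, set up by total injury rate. At a total of 4.49%, with half of all injuries (assumed) removed from one arm, the apparent ratio is (0.02245 / 0.97755) / 0.0449 = 0.51. The chance of meeting the rule goes from 13% to 46%, with 0.02245 × 107 = 2.4 women removed on average. Because events are few, a handful of exclusions is enough to move the result.

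**7. The opposite case.** Suppose all such women are kept, but only half of the control entry injuries ever surface, since control bladders are not filled. At *a* = 4%, *u* = 3%, the chance of meeting the rule falls from 8.4% to 4.2%. So the direction of the bias depends on the rule that is missing.

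**The case against.** The strongest reply is that the protocol already has the right order. The exclusion stands in an eligibility list, and the Randomisation procedure opens the envelope only once the woman is found eligible. The natural reading is a check made before allocation. Nothing tells anyone to repeat it afterwards, and the Outcome section counts injuries among subjects in each group with no exception for presumed timing. This stands. A reader might infer that the protocol prescribes removal after randomisation. It does not; it only fails to rule it out.

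Two further readings go too far. One is that injuries would be removed from one arm only. The dye test is available on suspicion in either group, so a control injury could also be judged to predate enrolment. Filling shows only injuries that leak, whereas the outcome definition includes muscle-layer injuries with intact mucosa, which would not be expected to leak. *Mainly* is therefore as far as the text goes. The other is that the principal surgeon is charged with dating injuries. No such step is written. What is written is that the same person enrols, learns the arm, operates and signs the form afterwards.

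The figures are also open to challenge. No document gives a rate of unseen entry injury, and 3% or 5% on its own is close to or above the highest total rate cited, 4.49%. Women selected for dense adhesions may well have higher totals, but nothing in the documents supports a particular unseen share. At 0.2% the effect is small (14% to 16%).

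What the reply does not remove is the wording by time of occurrence, the signature after the outcome is known, and the absence of any statement that allocated women stay in the analysis.

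**Conclusion.** The concern holds as a gap in the rules, not as a faulty procedure that the plan lays down. Applied literally after allocation, the exclusion could take outcome events mainly out of the cystoinflation arm and favour the intervention; the current text does not prevent this.

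The size is unknown. Under no true effect and a 4% adhesiolysis rate, the chance of meeting the 50% rule would go from about 13% to 18% at 0.5% unseen entry injuries and from 8% to 39% at 3%, or to 19% if half are removed. These figures depend on assumed rates, on removal that no passage orders, and on near-complete detection in control. They show sensitivity and are not estimates of the bias to expect in this trial.

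The point is worth settling before the first woman is randomised: it concerns who is counted in a primary outcome with few events, and the moment of injury cannot be reliably reconstructed after surgery.

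**What to change.** 1. Reword the criterion: *Women in whom a bladder injury is recognised before the envelope is opened are not enrolled; any injury recognised after the envelope is opened is counted in the allocated arm.*
2. Complete and sign eligibility on the Entry Form before the envelope is opened, with one new tick box: *bladder injury seen before envelope opened: yes/no*.
3. Record the moment of recognition and the presumed timing (entry or adhesiolysis) as descriptive items that do not affect who is analysed.
4. Report a sensitivity analysis that leaves out injuries first recognised before adhesiolysis began. Filling makes such recognition likelier in the cystoinflation arm, so this analysis leans towards the intervention. Read it beside the main analysis as the other end of a range.

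The cost is one sentence, one tick box, an earlier signature, two recorded items and one extra analysis. The statistical downside should be stated in the plan. Some entry injuries unrelated to adhesiolysis will be counted, which dilutes the contrast. They will not necessarily be counted equally: because filling can reveal leaks in one arm only, they may be found more often with cystoinflation, a conservative bias (8.4% to 4.2% in the example in step 7 of the working).

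### The surgeon who is to randomize the sample also grades adhesions, enrols and operates, so concealment of the next allocation is not secured

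*Combined protocol and SAP*

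**What the plan says.** **Who makes the allocation.** Randomisation procedure: "The Principal surgeon will randomize the calculated sample size into cysto-inflation and control groups by parallel assignment". An undefined plural subject then writes random numbers on the outside of closed envelopes that hold the group inside. "The closed envelopes will be serially placed with the smallest number uppermost, in random number file". Under Project Management, two co-investigators help to prepare the random numbers file. Both also counsel subjects, and one of them manages cystoinflation in theatre and performs follow-up.

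**Who enrols.** Under the second step of recruitment, residents start the operation and, on meeting dense adhesions, "the primary surgeons will hold the operation and call the principal surgeon". That surgeon grades the adhesions. Under Adhesiolysis, if the criteria are met, "the Principal surgeon will enrol her in the study as subject and perform randomization into cystoinflation and control groups". The same surgeon then completes the operation.

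**Safeguards.** "The file will be kept in the safe custody of theatre in-charge nurse before starting recruitment for the study". The nurse takes out and opens the top envelope once the woman has been recruited and tells the surgeon the group. The Data Destruction Plan keeps the list locked, without naming who has access.

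**The promise.** The Blinding section says that surgeons will not know the assignment before the operation. It also has the Principal surgeon send the number list to the statistician at the end of the study, with the groups recoded as letters.

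**Records.** "At the end of the operation, she will get the Entry Form signed by the Principal surgeon". Of the used envelope: "Then, she will close the envelope again and place it below all the envelopes".

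**The concern.** Allocation concealment means that whoever decides on entry cannot know or work out the next group. Here one person is assigned the randomization and also makes a partly subjective entry decision. If that person knows the next envelope, harder cases can be entered or passed over by arm, even without intent.

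Concealment matters more than usual in this trial. The operator cannot be blinded once adhesiolysis starts, and bladder injury is first detected by direct observation at surgery. Concealment before enrolment is the main protection left on the surgeon's side.

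The analysis could not repair selective entry. The regression in the Statistical analysis section could adjust for the recorded adhesion score, but the same surgeon assigns that score, and difficulty that the score does not capture would remain.

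**Working it through.** The plan gives no figure to reproduce on this point. The check traces the roles first. An illustration of size follows.

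**1. Can the next group be known?** The order of use is fixed by the numbers, smallest first. Anyone with the number-to-group list and a count of women enrolled can read off the next group. The Principal surgeon is named as the randomizer and supplies the recoded list at study end, so has the key at least by then. No section bars earlier access. If the undefined plural instead means the two co-investigators, one of them is still in theatre managing cystoinflation.

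**2. Is there room to select?** In the adhesion scoring table in the Background, dense adhesions score 4, 8 or 16. The threshold of 4 and above therefore excludes no dense case. What remains is largely judged by eye, for example "adhesions covering the bladder and lower segment of the uterus so that empty bladder will not be identified among the adhesions", or whether the lower segment can be reached without adhesiolysis. The Sample size section expects about 400 women with adhesions for 214 places, so declining some women need not stall recruitment.

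**3. Is the judgement fixed before the group is known?** Grading comes before randomization in the text, and the Entry Form lists grade and eligibility above the random number. But no time of writing is set, and the form is signed after the operation, when the group is known.

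**4. Illustration of size.** The documents give no injury rate for women with dense adhesions, so every risk and selectivity below is assumed. There is no true effect, and a woman who is passed over leaves the envelope on top.

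- *h* = share at high risk = 0.3; *r* = their relative risk = 3; *s* = proportion passed over = 0.3 to 0.5.
- One-way (high-risk women passed over when cystoinflation is next): cystoinflation high-risk share t = h(1−s) / [h(1−s) + 1−h]; control share c = h.
- Two-way (low-risk women also passed over when control is next): c = h / [h + (1−h)(1−s)].
- Expected risk ratio = [1 + t(r−1)] / [1 + c(r−1)], whatever the base risk.

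| Steering | s | t | c | Risk ratio |
|---|---|---|---|---|
| One-way | 0.3 | 0.21/0.91 = 0.231 | 0.300 | 1.462/1.600 = 0.913 |
| One-way | 0.5 | 0.15/0.85 = 0.176 | 0.300 | 1.353/1.600 = 0.846 |
| Two-way | 0.3 | 0.231 | 0.30/0.79 = 0.380 | 1.462/1.759 = 0.831 |
| Two-way | 0.5 | 0.176 | 0.30/0.65 = 0.462 | 1.353/1.923 = 0.704 |

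Over h = 0.2 to 0.4, r = 2 to 4 and s = 0.3 to 0.5, the one-way ratio runs from 0.96 to 0.80 and the two-way ratio from 0.91 to 0.64.

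The next table gives the chance of a false significant result favouring cystoinflation. It uses the pooled two-sided 5% z-test with 107 per arm, summed exactly over both binomials. Average risk without steering is 0.3 × high risk + 0.7 × low risk.

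| High / low risk | Average | No steering | One-way (s = 0.3; 0.5) | Two-way (s = 0.3; 0.5) |
|---|---|---|---|---|
| 6% / 2% | 3.2% | 2.2% | 2.9%; 3.5% | 3.7%; 5.8% |
| 15% / 5% | 8% | 2.6% | 4.0%; 5.4% | 6.1%; 11.8% |
| 30% / 10% | 16% | 2.5% | 4.7%; 7.5% | 8.6%; 20.3% |

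**The case against.** **The key link is inferred.** The surgeon's randomizing may mean only acting on an envelope that the nurse opens, and the undefined plural fits the co-investigators who are given the file to prepare. This stands as a limit. The text does not show that the surgeon knows the sequence, and the finding does not claim it. But the plan has to exclude that knowledge by procedure, and it does not.

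**The safeguards are real.** The nurse holds and opens the envelopes, and the list is locked. Using the order would take a retained list, or recall of 214 allocations, plus the current position. This lowers the risk. It does not remove knowledge gained in making the list, and nobody is named as barred from it.

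**The cases are triaged and witnessed.** Residents call the surgeon only for dense adhesions and can see the findings. That is some restraint, but the plan gives them no say in eligibility.

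**The missing fixed record is an argument from silence.** Signing at the end does not show that the entries were made then. That is fair. The point is only that nothing fixes them earlier.

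**The illustration is one-sided and can be extreme.** A surgeon who believes in the technique might steer harder cases into it. Reversing the two-way case gives risk ratios of 1/0.831 = 1.20 to 1/0.704 = 1.42, against cystoinflation. Two-way steering at 50% would also mean seeing 107/0.85 + 107/0.65 = about 290 women and passing over about 76 of them (26%), in front of residents and a nurse. Both points stand. The direction of any bias is unknown, and the 20.3% figure is an extreme case.

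**Counselling is peripheral.** It takes place before surgery, when neither the adhesions nor the top envelope is known. This also stands, and the conclusion does not depend on it.

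**Conclusion.** The concern holds and should be fixed before recruitment. The plan gives one surgeon the randomization, the grading, the entry decision and the operation, with envelopes used in a known order. It does not keep that surgeon from the list, so the promised concealment from surgeons is not secured. This conclusion comes from the text and needs no assumed figure.

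The size does rest on assumptions: the share at high risk, their relative risk, the selectivity and its direction. On the central inputs one-way steering is modest (risk ratio 0.91 to 0.85), and two-way steering is larger (0.83 to 0.70). No illustrated case reaches by expected bias alone the halving that the Project summary sets as its mark of effectiveness; the lowest ratio is 0.64. The concern is that a biased comparison could not be recognized or corrected afterwards.

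**What to change.** 1. **Independent sequence.** The independent statistician named under Blinding, or another person with no part in counselling, enrolment, surgery or follow-up, generates the sequence in A/B codes. That person prepares sequentially numbered, opaque, sealed envelopes and holds the list until database lock.
2. **Blinded statistician.** The theatre in-charge nurse holds the key to A and B. The statistician stays blinded, and the surgeon no longer needs to send a list at study end.
3. **Separation of roles.** The Principal surgeon and the two co-investigators named for the random numbers file neither prepare nor hold the list.
4. **Record before opening.** Before opening the envelope, the nurse writes down the surgeon's spoken adhesion grade and eligibility decision, with the time. The surgeon countersigns after the operation.
5. **Audit trail.** Opened envelopes are dated, signed by the nurse and filed, instead of being reclosed and returned to the stack. This is a secondary point.

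The single operating surgeon is kept. The cost is a change of protocol wording, to be submitted to the ethics committee because approval is already held, a few hours of the statistician's time by agreement with the other institution, and one timed entry by the nurse per woman while the operation is held. The scrubbed surgeon does no paperwork during the caesarean, and no extra patients or procedures are needed.
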